5.8.2 Key Secondary Efficacy Endpoints

CR rate, PFS, and changes in symptom domain per Skindex-29 assessment tool are designated as key secondary endpoints.

CR rate is defined as the proportion of patients who achieved a CR as their best response on study as determined by an IRF. A sensitivity analysis will be performed for CR per the investigator's GRS assessment. PFS is defined as the time from randomization until PD per IRF or death due to any cause, whichever occurs first. The symptom domain of Skindex-29 includes 7 items: 1) My skin hurts; 2) My skin condition burns or stings; 3) My skin itches; 4) Water bothers my skin conditions (bathing, washing hands); 5) My skin is irritated; 6) My skin is sensitive; and 7) My skin condition bleeds. The following scoring system is used for all items: never (0), rarely (1), sometimes (2), often (3), and always (4). The total score for all 7 items will be converted to a scale of 0 (no impact on quality of life) to 100 (maximum impact on quality of life) by linear transformation. The questionnaire is administered on Day 1 of Cycles 1, 2, 4, 6, 8, 10, 12, 14, and 16.

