4. STUDY DESIGN

4.1 Overview of Study Design

This is an open-label, randomized, multicenter study. All patients must have a diagnosis of MF or pcALCL and histologically-confirmed CD30+ disease by central laboratory assessment and pathology review. Patients are to be stratified by diagnosis: pcALCL or MF. Patients will enter 1 of 2 treatment arms:

- **Arm 1:** brentuximab vedotin monotherapy

Brentuximab vedotin (1.8 mg/kg) will be administered intravenously over approximately 30 minutes once every 21 days and may continue as monotherapy for up to a total of 16 cycles (48 weeks).

Brentuximab vedotin (SGN-35)

Clinical Study Protocol C25001 Amendment 5, EudraCT: 2010-024215-14

- **Arm 2:** methotrexate (MTX) or bexarotene per physician's choice, up to a total of 48 weeks treatment.

Methotrexate will be administered orally (5 to 50 mg) once weekly. Dose adjustment is guided by patient response and toxicity.

OR

Bexarotene will be administered orally (300 mg/m² recommended total dose per guidelines in [Figure 6-1](#)) once daily with meals.

Investigators are advised to consider a patient's prior treatment with reference therapy. It is recommended that patients who were last treated with methotrexate be treated with bexarotene, and patients who last received bexarotene be treated with methotrexate.

Objective response, lasting at least 4 months (ORR4), per independent review facility (IRF), will be assessed by global response score (GRS), which consists of skin evaluation (mSWAT assessment), nodal and visceral radiographic assessment, and detection of circulating Sézary cells (MF only). Objective response will be evaluated at the end of Cycles 3, 6, 9, 12, and 15, and at end of treatment (EOT). All treated patients without disease progression at EOT/ET will then be followed for objective response every 12 weeks for a minimum of 24 months, and then every 6 months; or until disease progression or study closure. CR or PR per GRS will be confirmed by sustained response in skin per mSWAT assessment at the subsequent cycle. Additional unscheduled GRS determinations may occur following a change in response in skin or at the time of a CT scan.

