5.8.1 Primary Efficacy Endpoint

The primary endpoint of this study is ORR4 per IRF. ORR4 per IRF is defined as the proportion of patients achieving an objective response that lasts at least 4 months (i.e., duration from first response to last response is ≥ 4 months) on study as determined by an IRF. Patients whose first response occurs after the start of subsequent anti-cancer therapy but otherwise meet the primary endpoint criteria will be excluded. For objective response, a patient must achieve a CR or PR. The objective response will be considered maintained for patients with a previous CR who experience recurrent disease (i.e. Relapse) unless the criteria for progressive disease are met. Determination of objective response will be based on a GRS, which consists of skin evaluation (mSWAT assessment) by investigator, nodal and visceral radiographic assessment by IRF, and detection of circulating Sézary cells (MF only) by IRF. Skin evaluation is done at screening, before dosing on Day 1 of Cycles 1, 2, and 3, at the end of every cycle beginning at Cycle 3, EOT, and at post treatment follow-up visits. Radiographic and blood assessments are less frequent due to ethical and logistical considerations.

For patients without nodal or visceral involvement (as determined by baseline CT scans), CT scans will be performed at screening and:

- During the cycle following the first skin response, ideally corresponding to the confirmation of the skin response, and 6 cycles (a minimum or 4 months) after that confirmed skin response.
- If there is a question of new or progressive disease in the LN/viscera

For patients with baseline nodal/visceral disease, CT scans will be performed at screening and:

- At the end of Cycles 3, 6, 9, 12, and 15, and per the follow-up schedule until disease progression
- If there is a question of new or progressive disease in the LN/viscera
- At EOT if the previous CT scan was performed more than 8 weeks before EOT

A blood sample for Sézary cell enumeration in patients with MF will be collected at screening; at the end of Cycles 3, 6, 9, 12, and 15, at EOT, and per the follow-up schedule until progressive disease or study closure.

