GRS will be determined by IRF at the end of each cycle beginning at Cycle 3, EOT, and at post treatment follow-up visits until disease progression, death or study closure. The GRS assessment at each cycle will incorporate the skin response at that cycle as well as the most recent nodal, visceral, and blood responses prior to or at the time of the GRS assessment time point. CR or PR per GRS will be confirmed by sustained response in skin per mSWAT assessment at the subsequent cycle.

For patients with skin only disease at baseline, GRS is essentially determined by skin response because disease progression in node/viscera/blood is atypical in the presence of a continuing skin response. In addition, the primary endpoint is further supported by CT confirmation of continued nodal/visceral noninvolvement at the cycle after the first skin response and 6 cycles after the first confirmed skin response. For patients with baseline nodal/viscera/blood involvement, GRS assessment at each cycle will incorporate the skin response at that cycle as well as nodal, visceral, and blood responses based upon the most recent respective compartment assessments prior to the GRS assessment time point. Blood results should be within 3 cycles. The CT scans should also be within 3 cycles for patients with nodal/viscera involvement.

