5.8.2.1 Analysis on Key Secondary Efficacy Endpoint

5.8.2.1.1 Handling of Missing Assessment and Censoring for Analysis of Progression-free Survival

Disease assessment data should be collected according to the intended schedule of assessment, and the date of PD/response should be assigned based on the time of the first documentation of PD/response regardless of violations or discontinuation of study drug.

For the PFS endpoint, patients who are lost to follow-up, withdraw consent, or those who discontinue treatment due to undocumented PD after the last adequate disease assessment will be censored at the last disease assessment. If death or PD occurs after a missed visit, then the patient is treated as progressed at the date of death or PD. Patients without baseline and/or no sufficient post baseline data for disease assessment and with no death recorded will be censored at the date of randomization. If PD is documented between scheduled visits, then the date of the documented PD is the date of progression. If the patient starts new antineoplastic therapy before PD, then the patient is treated as progressed at the date of assessment at which PD was documented.

The following sensitivity analyses will be performed for PFS to evaluate the robustness of treatment effects. They will be performed on the basis of 1 alteration at a time, not on combined alterations, unless specified otherwise.

- If the PD is documented between scheduled visits, then the date of the next scheduled visit is the date of progression.
- If treatment is discontinued for undocumented PD, then the patient is treated as progressed at the date of last disease assessment.
- Patients who start new antineoplastic therapy before PD will be censored at the date
 of the last disease assessment.
- Patients who start new antineoplastic therapy before PD will be treated as progressed at the date of the last disease assessment.
- If death or PD occurs after more than 1 missed visit, then the patient will also be censored at the last disease assessment before the missed visits.

Another sensitivity analysis will be conducted for PFS per IRF in the ITT population to assess the robustness of the primary analysis's use of most recently available CT scans and

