5.8.2.1.2 Key Secondary Efficacy Analysis

Because a fixed sequential testing procedure is used between the primary endpoint and the key secondary endpoints, the key secondary endpoints will be tested only if the primary endpoint is statistically significant. The weighted Holm procedure⁽¹⁾ will be used for testing the key secondary endpoints. See Section 3.2 for details of the statistical decision rules.

Stratified log-rank test statistics will be used to compare PFS between the 2 treatment arms. The hazard ratios along with the 95% CIs will be estimated using a stratified Cox regression model. The Kaplan-Meier method will be used to estimate the distribution of the time-to-event endpoints for each treatment. Median times (if estimable), along with the 2-sided 95% CIs, will be presented.

Assuming the median PFS for the brentuximab vedotin treatment group and the physician's choice treatment group (MTX or bexarotene) are 9 and 6 months, respectively, the number of PFS events is projected to be approximately 101 at the time of the planned final analysis. This is based on an approximately 2-year enrollment period, a dropout rate of 10%, and an α level of 0.01 (2-sided), as specified in Section 3.2 per the weighted Holm procedure.

Comparison of the CR rates between the 2 treatment groups will be conducted using the stratified Cochran-Mantel-Haenszel test. The 95% CI of the difference in the response rates between the 2 treatments will also be provided. No imputation will be conducted for missing data. Patients who do not have any post baseline response assessment as specified in the protocol will be counted as nonresponders.

For skin symptoms (Skindex-29), the primary analysis will be comparing the mean symptom reduction between brentuximab vedotin and the control arms. 'Symptom reduction' is defined for each patient as the maximum reduction from baseline (sum of the 7 items related to skin symptoms normalized to a 1-100 scale). The analysis of covariance (ANCOVA) model controlling for baseline covariates (treatment group, baseline score, disease diagnosis, ECOG) will be employed for the analysis. As a sensitivity analysis, comparison of the 2 treatment groups will be conducted using the linear mixed model with repeated measures at

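### The CR-rate definition in SAP 5.8.2 does not exclude a CR first reached after subsequent anti-cancer therapy, although ORR4 bars first responses reached that way

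*SAP*

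**What the plan says.** **CR rate.** SAP 5.8.2: "CR rate is defined as the proportion of patients who achieved a CR as their best response on study as determined by an IRF". SAP 5.8.2.1.2 adds one rule on who is a non-CR: "Patients who do not have any post baseline response assessment as specified in the protocol will be counted as nonresponders". Protocol 8.1.6.2 adds none, and SAP section 6 lists no change from the protocol.

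**ORR4.** SAP 5.8.1 also speaks of response on study, but adds a limit: "Patients whose first response occurs after the start of subsequent anti-cancer therapy but otherwise meet the primary endpoint criteria will be excluded".

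**How long response is scored.** SAP 5.8.1: "GRS will be determined by IRF at the end of each cycle beginning at Cycle 3, EOT, and at post treatment follow-up visits". The sentence then names progression, death and study closure as the end points; the start of other therapy is not one. Protocol 4.1: "All treated patients without disease progression at EOT/ET will then be followed for objective response every 12 weeks for a minimum of 24 months".

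**How other endpoints treat new therapy.** For PFS, SAP 5.8.2.1.1 follows the patient through it and takes the later visit that records progression as the event: "If the patient starts new antineoplastic therapy before PD, then the patient is treated as progressed at the date of assessment". Two PFS sensitivity analyses vary that choice. EFS, duration of response and duration of skin response each have a rule in SAP 5.8.3.1.

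**Planned CR sensitivity analyses.** There are two: investigator assessment (SAP 5.8.2) and the Response-Evaluable population (SAP 5.8.2.1.2).

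**The concern.** CR rate is a confirmatory endpoint. SAP 3.2 gives it weight 0.7 in the weighted Holm procedure, against 0.2 for PFS and 0.1 for the Skindex-29 symptom domain. A best response with no stop at new therapy lets a CR produced by a different treatment count for the randomised arm.

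The exposed patients are those who stop study drug without IRF-documented PD (toxicity, stable disease, completion of 48 weeks, or suspected PD that the IRF did not confirm) and then start something else. The plan expects such patients. Protocol 7.7 keeps those who stop early without PD in post-treatment assessment, and protocol 4.3 foresees subsequent standard-of-care therapy after 48 weeks of reference therapy. For the brentuximab vedotin arm, protocol 4.3 mentions possible further access to brentuximab vedotin instead, so what follows study treatment may differ by arm.

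Both CR sensitivity analyses keep the same open time window, so neither would show whether the result depends on these patients.

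**Working it through.** **1. The plan's own figures.** SAP 3.2 gives weighted Holm powers of 82% (CR), 48% (PFS), 40% (Skindex-29) and 84% (at least one). Inputs, all from SAP 3.2: success probabilities 0.85, 0.55 and 0.50 at two-sided 0.05; correlation 0.5; weights 0.7, 0.2 and 0.1. A simulation of 1,000,000 trivariate normal draws, with each mean set to Φ⁻¹(success probability) + 1.96, gives 81.7%, 48.2%, 40.6% and 83.5%. The figures reproduce. The point concerns who counts as a CR and corrects no stated number.

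**2. Is a post-switch CR inside the definition?**
- Scoring does not stop at new therapy (SAP 5.8.1).
- Response is dated "based on the time of the first documentation of PD/response regardless of violations or discontinuation of study drug" (SAP 5.8.2.1.1).
- The PFS rule uses PD documented after new therapy, so assessments are expected to continue past a switch.
- ORR4 uses the same term, on study, and still needed an explicit exclusion. If the term already ended at new therapy, that sentence would have nothing to do.
- No sentence in SAP 5.8.2, SAP 5.8.2.1.2 or protocol 8.1.6.2 removes such a CR.

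**3. Is there time for it?** Enrolment is planned at 24 months, with the final analysis 10 months after the last patient, about 34 months from study start (protocol 4.3). Treatment lasts up to 48 weeks, or 48 × 7 / 30.44 ≈ 11 months. The earliest patients could be about 34 − 11 = 23 months past a full course; the last enrolled would still be within their 48 weeks. The window is real for early enrollees and for early stoppers, and small for late enrollees.

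**4. Threshold for CR.**
- First step: 0.7 × 0.05 / (0.7 + 0.2 + 0.1) = 0.035.
- If only Skindex-29 has already been rejected: 0.7 × 0.05 / 0.9 = 0.039.
- If only PFS has: 0.7 × 0.05 / 0.8 = 0.044.
- If both have: 0.05.

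**5. Sensitivity to a few patients (counts assumed).** With n = 62 per arm, N = 124 and CR counts a and b, the unstratified chi-square without continuity correction is X² = N[a(n−b) − b(n−a)]² / [n²(a+b)(N−a−b)].

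| CRs, brentuximab vs control | X² | two-sided p |
|---|---|---|
| 14 vs 4 | 124 × 620² / (62² × 18 × 106) = 6.50 | 0.011 |
| 14 vs 5 | 124 × 558² / (62² × 19 × 105) = 5.03 | 0.025 |
| 14 vs 6 | 124 × 496² / (62² × 20 × 104) = 3.82 | 0.051 |
| 14 vs 7 | 124 × 434² / (62² × 21 × 103) = 2.81 | 0.094 |

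In this example one added control CR changes nothing, while two or three lose the result at every Holm step. The opposite direction is also possible. With the single-stratum Mantel-Haenszel form (X² × 123/124), 6 vs 1 gives p = 0.053 and 7 vs 1 gives p = 0.029, so one added brentuximab CR can create a first-step rejection.

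**6. How many could be added?** The documents give no number of switchers. Assume 6 of 62 in one arm. CR rates that the protocol cites for other therapies are 22% (gemcitabine), about 43% (pegylated liposomal doxorubicin) and 50% (total skin electron beam therapy, 18 retrospective cases). The product is 6 × 0.22 = 1.3 to 6 × 0.50 = 3.0 CRs, or 2 to 5 percentage points of 62.

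**7. Effect on first-step power (assumed rates).** Take control CR rates of 2% to 15%, the brentuximab rate that gives 85% power at 0.05, and α = 0.035. First-step power is then 81%.

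| Share of one arm credited with a post-switch CR | Power if control is credited | Power if brentuximab is credited |
|---|---|---|
| 2% | 65–72% | about 87% |
| 3% | 56–67% | about 89% |
| 5% | 39–57% | about 93% |

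**The case against.** **The SAP is silent, and the term on study is undefined.** SAP 5.11.1.3 lists deaths on study and during follow-up as if they were separate, and SAP 5.7.1 speaks of an on-study period for concomitant medication. On that usage many post-switch CRs would fall outside the definition. This stands in part: a reader might infer that the SAP expressly counts such CRs, and it does not. It fails to exclude them. The wider meaning is still the better reading, because protocol 7.6 and 7.7 keep patients on study during follow-up and the ORR4 sentence presupposes it.

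**Ignoring new therapy may be intended.** PFS does so, and a treatment-policy CR rate is a coherent quantity. But the SAP does not state that intention for CR, the primary endpoint takes the other approach for first responses, and PFS has sensitivity analyses for new therapy where CR has none.

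**The comparison with ORR4 covers only one of two cases.** A reader might infer that a PR on study drug that becomes a CR after a switch also contradicts ORR4. It does not, because ORR4 looks only at the first response. Covering that case is a further choice.

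**Exposure is limited.** Scoring ends at PD, so it would be wrong to infer that patients who progress and then switch are credited. Investigators are encouraged to await independent review when PD is suspected (protocol 7.7), other CTCL therapy is prohibited during the study (protocol 6.5), and CR needs a sustained skin response at the next cycle while off-treatment visits are 12 weeks apart. These lower the frequency. None is an analysis rule, and the SAP itself provides for new therapy before PD.

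**The example is constructed.** This is correct. The counts were chosen near the threshold, and the 50% rate comes from a small series of advanced refractory disease rather than from confirmed IRF responses in patients who stopped without PD.

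**Conclusion.** The point holds as a gap in the definition of a confirmatory endpoint. As written, SAP 5.8.2 does not exclude a CR first reached after subsequent therapy, and the assessment schedule makes such a CR observable in patients who switch without IRF-documented PD. No planned CR analysis isolates it.

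Its size cannot be derived from the documents. The p-values and power ranges rest on assumed CR rates, assumed numbers of switchers, 62 per arm and, for the p-values, an unstratified test in place of the planned stratified one. They show that two or three patients, sometimes one, can change a borderline result. They do not show that this is likely, nor that either arm is favoured: the direction depends on which arm has more switching without PD and how effective the later therapy is. The sample size of 124, the Holm weights and the stated powers are unaffected.

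**What to change.** In SAP 5.8.2, count a patient as a CR only if the GRS CR per IRF is first documented before the start of any subsequent anti-cancer therapy. Keep all other ITT patients in the denominator as non-CR. This should be explicit, because the ORR4 sentence says only that such patients are excluded, without saying from what. Report the current any-time count as a sensitivity analysis.

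This is deliberately stricter than the ORR4 wording. Copying that sentence would still credit a PR on study drug that turns into a CR only after a switch.

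The SAP should also state whether brentuximab vedotin given after the 16 study cycles, which protocol 4.3 allows for, counts as subsequent therapy under this rule.

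The cost is a few lines of SAP text and one extra table. The therapy start date is already needed for ORR4, EFS and the PFS sensitivity analyses. The downside is that the CR count may fall slightly in one or both arms.

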5.8.2.1 Analysis on Key Secondary Efficacy Endpoint

5.8.2.1.1 Handling of Missing Assessment and Censoring for Analysis of Progression-free Survival

Disease assessment data should be collected according to the intended schedule of assessment, and the date of PD/response should be assigned based on the time of the first documentation of PD/response regardless of violations or discontinuation of study drug.

For the PFS endpoint, patients who are lost to follow-up, withdraw consent, or those who discontinue treatment due to undocumented PD after the last adequate disease assessment will be censored at the last disease assessment. If death or PD occurs after a missed visit, then the patient is treated as progressed at the date of death or PD. Patients without baseline and/or no sufficient post baseline data for disease assessment and with no death recorded will be censored at the date of randomization. If PD is documented between scheduled visits, then the date of the documented PD is the date of progression. If the patient starts new antineoplastic therapy before PD, then the patient is treated as progressed at the date of assessment at which PD was documented.

The following sensitivity analyses will be performed for PFS to evaluate the robustness of treatment effects. They will be performed on the basis of 1 alteration at a time, not on combined alterations, unless specified otherwise.

- If the PD is documented between scheduled visits, then the date of the next scheduled visit is the date of progression.
- If treatment is discontinued for undocumented PD, then the patient is treated as progressed at the date of last disease assessment.
- Patients who start new antineoplastic therapy before PD will be censored at the date
 of the last disease assessment.
- Patients who start new antineoplastic therapy before PD will be treated as progressed at the date of the last disease assessment.
- If death or PD occurs after more than 1 missed visit, then the patient will also be censored at the last disease assessment before the missed visits.

Another sensitivity analysis will be conducted for PFS per IRF in the ITT population to assess the robustness of the primary analysis's use of most recently available CT scans and

blood assessments for GRS. For patients with baseline nodal/visceral/blood disease, the sensitivity analysis will only use GRS assessed at time points with concurrent nodal/viscera/blood component assessments as specified in the protocol SOE while for patients with skin-only disease, the analysis will use the same GRS assessment frequency as the primary analysis.

